We will plan to use a recruitment method referred to as respondent-driven sampling, or "seed recruitment" ([name]., personal communication). Seed recruitment is suitable for sampling "hidden populations" of participants who are best known by their own peers (Heckathorn, 1997). It includes providing incentives to participants for referral of other eligible participants. In our model, each participant, or seed, will receive a coupon to recruit another person in his/her social networks. The recruitment coupon will provide a brief description of the survey and a phone number for contacting the study coordinator. The coupon will be marked with a unique identification number (not the study identification number) so that when the coupons are returned to us, the ID number can be used to provide payment (\$20) to the participant who made the referral. The key connecting the participant's study ID number with the seed ID number will be kept in a database separate from other PHI, creating two layers of separation between the seed ID and the already-participating person's identifying information. Any participant who does not wish to recruit in this manner will not be required to do so.

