lead to positive changes in cannabis users' functional outcomes. The R33 study will be directly modeled after the R21 study and will use the final reinforcement schedule developed through the R21 as well as the same recruitment, enrollment, and screening procedures described herein. Based on evaluation of the R21 data, we have modified the contingency management procedures such that participants are

| Table 2. R33 Phase potential payment schedule with "free day" allowance | | | | | | | | | |
|---|------|---------------|--|----------|----------------------------|--|------------------|---------------|--|
| Week | Day | Saliva videos | (Regardless of use) Daily Saliva Video Uploads | Smoking? | Daily Saliva Video Uploads | Explanation | Total | Running Total | |
| Week 1 & 2 (Ad Lib) | 1-14 | 1 | \$2.50 | As Usual | No Bonus yet | \$5.00 (\$2.50 per video) payment for uploading saliva testing videos (regardless of cannabis use). \$5 for providing a self-initiated reading. | \$10.00 each day | \$140.00 | |
| | | 2 | \$2.50 | As Usual | | | | | |
| | | SI* | \$5.00 | As Usual | | | | | |
| Weeks 3 to 7 (CM Phase 1), one example week shown | 15 | 1 | \$2.50 | No | \$10.00 | Participants will earn \$10 for their first day of verified abstinence. \$1 bonus marijuana payment for verified marijuana-free day or if the once-a-week cheat day is used. | \$15.00 | \$155.00 | |
| | | 2 | \$2.50 | No | | | | | |
| | 16 | 1 | \$2.50 | No | \$11.00 | | \$16.00 | \$171.00 | |
| | | 2 | \$2.50 | No | | | | | |
| | 17 | 1 | \$2.50 | No | \$12.00 | | \$17.00 | \$188.00 | |
| | | 2 | \$2.50 | No | | | | | |
| | 18 | 1 | \$2.50 | No | \$13.00 | | \$18.00 | \$206.00 | |
| | | 2 | \$2.50 | No | | | | | |
| | 19 | 1 | \$2.50 | Yes | \$14.00 | | \$19.00 | \$225.00 | |
| | | 2 | \$2.50 | Yes | | | | | |
| | 20 | 1 | \$2.50 | No | \$15.00 | | \$20.00 | \$245.00 | |
| | | 2 | \$2.50 | No | | | | | |
| | 21 | 1 | \$2.50 | No | \$16.00 | | \$21.00 | \$266.00 | |
| | | 2 | \$2.50 | No | | | | | |
| Week 8 (CM Phase 6) | 50 | 1 | \$2.50 | No | \$45.00 | 1 dollar increase to bonus marijuana payment for verified marijuana-free day or if the once-a-week cheat day is used. | \$50.00 | \$1310.00 | |
| | | 2 | \$2.50 | No | | | | | |
| | 51 | 1 | \$2.50 | No | \$46.00 | | \$51.00 | \$1361.00 | |
| | | 2 | \$2.50 | No | | | | | |
| | 52 | 1 | \$2.50 | No | \$47.00 | | \$52.00 | \$1413.00 | |
| | | 2 | \$2.50 | No | | | | | |
| | 53 | 1 | \$2.50 | No | \$48.00 | | \$53.00 | \$1466.00 | |

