| | | 2 | \$2.50 | No | | | | | |
| 54 | 1 | \$2.50 | Yes | | \$49.00 | | \$54.00 | \$1520.00 | |
| | | 2 | \$2.50 | Yes | | | | | |
| | 55 | 1 | \$2.50 | No | \$50.00 | | \$55.00 | \$1575.00 | |
| | | 2 | \$2.50 | No | | | | | |
| 56 | 1 | \$2.50 | No | | \$51.00 | | \$56.00 | \$1631.00 | |
| | 2 | \$2.50 | No | | | | | | |

only asked to respond to two daily alarms (instead of three). Note, this decreases the potential amount of money earned.

Seventy-two participants will be randomized using a 2:1 allocation ratio to either the Reduced Use

Condition (n = 48) or a Control Condition (n = 24). Inclusion of a control group will allow clear inferences to be drawn regarding the effects of reduced cannabis use on functional outcomes. Study participation will entail completion of the baseline assessment, completion of the 8-week EMA study, and completion of the 8-week follow-up assessment.

D.2. R33 Inclusion/Exclusion Criteria and Recruitment

Timeline

The final inclusion/exclusion criteria for the R33 phase of project will be identical to the R21 inclusion/exclusion criteria with one exception: Participants who are found to meet criteria for bio-verified sustained abstinence (i.e., all of their saliva tests are negative during the 6-week experimental phase of the study) will be excluded from the statistical analyses to ensure that there is an upper limit on reduced use. Thus, we will exclude any participants who achieve sustained abstinence to ensure that any improvements in functioning observed among participants in the experimental condition are not being driven by inclusion of a subset of participants who achieve sustained abstinence. Please also note that we can exclude up to 12 of the 72 enrolled participants from the statistical analyses (remaining N = 60) and still be adequately powered to conduct all of the proposed analyses.

[figure not shown]
D.3. Diagnostic Reliability and Training of Clinical Interviewers

Interviewers will be trained to conduct the interviews using our standardized laboratory procedures, including rating videotaped interviews and participation in ongoing weekly supervision. These procedures have produced consistently high interrater reliability, with Fleiss' kappa values ranging from .92-.94 in previous studies (Kimbrel, Newins et al., 2017; Kimbrel, Calhoun et al., 2014).

D.4. Participant Reimbursement

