In addition to the compensation that participants will receive from the CM procedures, participants will also receive \$75 for completion of the baseline assessment, \$25 for the post *ad lib* period urine testing, \$150 for the 8-week follow-up, and \$400 for the EMA study (\$50 per week). They will also be eligible to receive a \$25 bonus per week for not missing more than 1 EMA alarm per day, and a \$50 bonus for returning their equipment on time. These procedures have worked well (high compliance and equipment return rates) in previous studies (Carpenter et al., 2015; Hertzberg et al., 2013; Beckham, Calhoun et al., 2013; Dennis et al., 2016; Volz et al., 2014). Participants may also receive \$20 for successfully recruiting another participant in his/her/their social network.

Figure 2. R33 Study Design & Participant Flow

D.5. Description and Timing of In-Person Assessments

Table 2 describes the laboratory and self-report assessments that will be collected at the baseline and 8-week follow-up assessments as well as their administration schedule. Whenever possible, we have selected Common Data Elements from the PhenX Toolkit (Hamilton et al., 2011) to maximize the impact of the proposed research. We have also elected to use brief measures when possible to reduce burden. Whenever possible, participants will complete questionnaires remotely using Duke's instance of RedCap.

D.6. EMA and CM Procedures

EMA addresses the limitations of traditional assessment techniques by (a) repeatedly assessing participants in their normal daily environment, which enhances ecological validity; (b) assessing experiences and behaviors at the time they occur, which minimizes memory biases associated with retrospective recall; and (c) allowing for examination of the context of participants' experiences.

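### R33 keeps paid referral within social networks but randomises each person individually, so about 44% of any referral pairs will be split between arms, and nothing separates their study periods or uses the stored link

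*Combined protocol and SAP*

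**What the plan says.** C.4 (Recruitment & Enrollment) sets up respondent-driven recruitment for R21: "each participant, or seed, will receive a coupon to recruit another person in his/her social networks". The referrer is paid $20. Taking part is optional: "Any participant who does not wish to recruit in this manner will not be required to do so". The key joining a participant's "study ID number with the seed ID number will be kept in a database separate from other PHI", so the study can tell who referred whom.

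D.1 carries this into R33, which uses "the same recruitment, enrollment, and screening procedures described herein". D.4 repeats the $20 payment among the R33 reimbursements, "for successfully recruiting another participant in his/her/their social network".

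D.1 also sets the allocation: "Seventy-two participants will be randomized using a 2:1 allocation ratio", giving 48 in the Reduced Use Condition and 24 in the Control Condition. It describes no pair, household or network as a unit of allocation.

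Under D.6 both groups complete two ad lib weeks. For the next six weeks the Reduced Use group is paid for verified abstinence, while controls receive yoked payments that do not depend on their own use.

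E.3 describes two kinds of model. One has treatment group, week and their interaction, with day or week at Level 1 and the person at Level 2. The other relates outcomes to the week-by-week reduction achieved, ignoring treatment group. Neither has a term for referral links. No section discusses contact between participants in different conditions.

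**The concern.** In the single-arm R21 phase it did not matter if two friends took part together, because there was no comparison to disturb. In R33 the same recruitment text sits on top of individual randomisation. A participant and the friend they bring in can land in opposite conditions and be in the study at the same time.

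The friend must be eligible, and C.3 defines that as non-edible cannabis use on at least 40 of the past 90 days. The pair are therefore two heavy users who know each other, and one of them may be paid to abstain. The control may cut down alongside the paid friend, or the paid friend may be drawn back to use by the control. Either would narrow the difference in use between the arms.

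That difference is what lets the treatment-by-week comparison speak to the effect of reduced use, which D.1 gives as the reason for having a control group. If it narrows, the between-arm effect on functioning is understated. A null result could then not be told apart from linked controls having changed their use as well.

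**Working it through.** The plan gives no figure for referrals, contact between arms or loss of contrast, so there is nothing of its own to reproduce on this point.

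**Inputs from the documents**
- 72 participants: 48 Reduced Use and 24 Control (D.1)
- One coupon per participant (C.4)
- Two ad lib weeks and six experimental weeks (D.6)

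**Inputs the documents do not give (assumed)**
- *m*: number of R33 participants who enrol on the coupon of another R33 participant
- *c*: fraction of the paid friend's reduction that a linked control adopts
- *v*: fraction of the six experimental weeks that the pair share

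**Step 1: chance that a pair is split.** With independent 2:1 allocation this is 2 × 2/3 × 1/3 = 4/9 = 44.4%. With totals fixed at 48 and 24 it is 2 × 48 × 24 / (72 × 71) = 2304/5112 = 45.1%. This holds for each pair, however many pairs there are.

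**Step 2: which arm is more exposed.** A control with one referral partner has a 2/3 chance (48/71 = 67.6% with fixed totals) that the partner is in Reduced Use. For a Reduced Use participant the chance of a control partner is 1/3 (24/71 = 33.8%).

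**Step 3: share of controls in a split pair.** *s* = *m* × (4/9) / 24. This is an upper figure, because it assumes that each split pair involves a different control.

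**Step 4: loss of contrast.** Suppose the Reduced Use arm lowers use by R and unlinked controls do not change. The mean reduction among controls is then *s* × *c* × *v* × R. The contrast becomes R × (1 − *s* × *c* × *v*), so the proportional loss is *s* × *c* × *v*. This counts only controls who follow the paid friend; influence in the other direction would add to it.

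| Referrals *m* | Split pairs | Share of 24 controls *s* | Carry-over *c* | Overlap *v* | Loss |
|---|---|---|---|---|---|
| 4 | 1.8 | 7.4% | 25% | full | 1.9% |
| 10 | 4.4 | 18.5% | 50% | full | 9.3% |
| 18 | 8.0 | 33.3% | 50% | half | 8.3% |
| 18 | 8.0 | 33.3% | 50% | full | 16.7% |

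Half overlap corresponds to the friend starting three weeks after the referrer, which leaves 6 − 3 = 3 of the six experimental weeks in common. Overlap therefore matters as much as carry-over, and the documents do not say when the coupon is handed out.

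**Step 5: which E.3 analysis is affected.** In the treatment-by-week model, a control who cuts down still counts as a control, so the contrast is diluted. In the model of achieved reduction, the same person is counted by what they actually did, so this route does not dilute the estimate in the same way. That model compares self-selected levels of reduction, so it does not have the protection of randomisation, and it also ignores any correlation within referral pairs.

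**The case against.** Five points can fairly be made on the other side.

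1. The number of pairs may be small. Referral is voluntary, with one coupon each, and it sits beside clinic and community flyers, record searches with letters and calls, newspaper and online notices, and social media advertising (C.4). This stands. It is why the range must include a low case.

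2. Overlap may be partial. A referred friend must phone, be screened, attend a visit, practise for 24 hours and complete two ad lib weeks. This also stands, and the third row of the table shows its effect.

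3. Controls already know about the payments, since consent explains the study in detail, and every participant must be willing to try to reduce use (C.3, C.4). That weakens the idea that a control learns something new from the friend. It does not deal with friends who use together. Joint use is, however, an inference and not something the documents state.

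4. Controls report use daily, so a fall in their use would be visible. True, but without the referral link it could not be traced to contact with the other arm.

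5. Hypotheses 1a and 1b concern decreased use, so the model of achieved reduction is not a side analysis, and it is less exposed. This stands, and it limits the point to the randomised comparison.

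A reader might go further and infer that E.5's detectable effect of d = 0.30 shrinks by a known amount, with a matching fall in power. The documents do not support that. The figure of 0.30 is what E.5 says can be detected, not an expected effect. Its 420 observations are 60 participants × 7 weekly values, counted as the effective sample size for a factor that varies only between people. Any power figure built on these, with assumed referrals and assumed influence, would be false precision.

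**Conclusion.** The gap is real. Paid referral within social networks applies in R33, allocation is by individual, and about 44% of any referral pairs (45% with fixed totals) will be split. The plan neither separates linked participants in time nor uses the link it holds.

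The consequence is conditional. If linked participants influence each other's use while both are enrolled, the treatment-by-week contrast is biased toward zero. Its size cannot be determined from the documents. With full overlap, the illustrative loss is about 2% for 4 referrals and 25% carry-over, and about 17% for 18 referrals and 50% carry-over. Shorter overlap lowers both in proportion. The referral counts, carry-over and overlap are all assumptions.

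Two broader conclusions may tempt a reader. One is that the contrast will shrink materially; the documents do not show this, because they record no referral count and no evidence of peer influence. The other is that every estimate of the functional effect is understated; this does not follow either, because E.3's achieved-reduction model is not diluted in the same way.

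This is an optional, low-cost improvement and not a flaw that undermines the trial.

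**What to change.** - **Coupon timing.** In R33, issue the recruitment coupon at the 8-week visit, so that the referrer has finished before the referred person starts.
- **Referral flag.** Use the existing seed key to mark, in the analysis data, each participant who referred or was referred by another R33 participant, with the dates of both study periods.
- **Sensitivity analysis.** Rerun the E.3 treatment-by-week model without participants whose study period overlapped that of a linked participant in the other condition. Report it as supportive only: it excludes people after randomisation, and with 24 controls it may be imprecise. In the 18-referral illustration it could remove up to 8 controls and their 8 partners.

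The cost is a change of recruitment wording, one derived flag and one extra model run. Referrals would arrive up to about 8 weeks later, which may slow enrolment. The change ends concurrent participation in split pairs, but it does not stop a referrer who has finished from talking to a friend who is still enrolled. For anyone already enrolled when the change is made, the flag and the sensitivity analysis remain possible from the stored key.

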Milestone 3: We will calculate the association between frequency of cannabis use (days) and total quantity of cannabis consumed per week based on participants' EMA data concerning quantity of cannabis use.

If the proposed R21 milestones are met, we will complete the following specific aims during the R33 phase:

R33 Aim 1: Assess the impact of reduced frequency and quantity of cannabis use on functioning.

Hypothesis 1a: Decreased cannabis use will be associated with significant improvements in mental health symptoms, self-efficacy, physical activity, and health-related quality of life.

Hypothesis 1b: Decreased cannabis use will be associated with significant improvements in working memory, impulsivity, and drugged driving.

R33 Supplementary Aim: Explore momentary (e.g., craving, sleep) and between-person factors (e.g., sex, baseline use) that might moderate the association between cannabis use and functioning.

Expected Outcomes: The proposed research will be the first study to systematically assess the impact of reduced frequency and quantity of cannabis use on functioning. As such, these findings will directly inform ongoing efforts to include reductions in illicit drug use as a valid, clinically-meaningful outcome measure in clinical trials of pharmacotherapies for the treatment of CUD and other substance use disorders (Tiffany et al., 2011; Donovan et al., 2011).

A. SIGNIFICANCE

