| Timeline Followback of Drugged Driving (Robinson, Sobell, Sobell, & Leo, 2014) | Participants will be asked to report days they have driven within 2 hours of using cannabis use in the past 28 days using Timeline Followback method. | X | | X |
| Sound Sensitivity Measures (Hiller & Goebel, 1992; Khalfa et al., 2002; Wu et al., 2014) | Several measures, including the Mini Tinnitus Questionnaire, Misophonia Questionnaire, and Hyperacusis Questionnaire, will measure sound sensitivity. | X | | |

D.6.1. Electronic Diary System Hardware and Data Security. We have established methods to limit risk of breach of confidentiality in EMA studies (Carpenter et al., 2015; Hertzberg et al., 2013; Beckham, Calhoun et al., 2013; Dennis et al., 2016; Volz, et al., 2014). The smart phone used will be any one of four models of Droid phones: 1) Droid Turbo 2 (Motorola Mobility Inc, Libertyville, IL) with a Qualcomm Snapdragon 810 processor, 5.4" Quad HD display; 2)Droid Turbo, with 5.2" Quad HD Super AMOLED™ Corning® Gorilla® Glass 3 Display; 3) Droid MAXX, with a dual-core 1.2 Ghz processor, 1 GB DDR2 RAM, and 4.3" gHD display; or 4) Droid MAXX 2 DROID MAXX 2 with an octa-core 1.7 Ghz processor, 2 GB RAM, and 5.5" full HD display. Each will be equipped with an Android operating system that is compliant with Federal Information Processing Standard (FIPS) 140-2 standards. Features other than the electronic diary, calling, and texting features will be locked out. The phone will be programmed so that staff can set up the phone by simply entering a participant's code. Encrypted TLS connections will be used to upload data to the server. The study's website will use a Virtual Private Server provided by InMotion Hosting, Inc. The data at InMotion Hosting are Advanced Encryption Standard (AES)-256 encrypted at rest, and the data being transferred are encrypted at transfer AES-256 & Transport Layer Security (TLS). Website properties include TLS 1.0, AES w/ 128 bit encryption (High); Rivest-Shamir-Adleman (RSA) with 2048 bit exchange. The web application written for this study has been checked for SQL injection, Code Injection, XSS, and RFI vulnerabilities and has passed. The site will only be

accessible to staff via 512-bit SHA-2 hashed passwords.

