Participants will be asked at each EMA assessment if they have used cannabis, alcohol, or any other illicit drugs, and, if so, how much of each substance they used. Participants will also be prompted each night (~11pm) to estimate the total amount of cannabis, alcohol, and illicit drugs they used in the past 24 hours. Quantity and potency of cannabis consumed during each EMA assessment will be calculated using van der Pol's methods (van der Pol et al., 2014). Participants will also be given a small scale to use to measure their marijuana stash at the end of each day (to assist them in estimating daily use). If participants report use, they will also be asked if they drove a vehicle within two hours of use. We will also ask participants to report the total number of times they engaged in any form of drugged driving during the past 24 hours at the end of each night. EMA-based assessment of cannabis craving will use an 11-point Likert scale that ranges from 0 = "No urge" to 10 = "Extreme urge" (Buckner et al., 2012). EMA of cannabis withdrawal will be completed with the Marijuana Withdrawal Checklist (Budney, Novy & Hughes, 1999; Budney et al., 2003). In our review of data from the first cohorts, we noticed that participants who do not do at least 10 of the 14 nighttime diary readings during the ad lib period are much less likely to participate in the study fully, and are much more likely to be lost to contact during the treatment phase. Therefore, we would like to include in the treatment phase only those participants who complete 10 of the 14 nightly diaries. Any participant who does not meet this criterion will be withdrawn from the study.

EMA of physical activity will be conducted with the Fitbit Charge 2, a light-weight wristband capable of tracking steps, calorie consumption, and sleep. The Vivofit has been validated previously (Simunek et al., in press) and features a 1-year battery life, making it an attractive alternative to more expensive devices. Our programmer, [name], has already written a program that enables us to capture participants' daily step data via Fitbit's Bluetooth syncing technology.

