During the 8-week EMA data collection, we will calculate the percentage of responses recorded within 5 minutes of the random prompts. We will exclude responses delayed by longer than 5 minutes from the analyses. Data will be aggregated at the day-to-day level to indicate the following: whether cannabis was used; the total number of joints/grams consumed; mean daily potency; mean daily levels of mental health symptoms, self-efficacy, health-related quality of life, working memory, and impulsivity; whether participants drove while intoxicated; and total amount of physical activity. By using multi-daily records to examine day-level phenomena, we will minimize measurement error related to poor recall and random variability. For the 2-week baseline period and each week of the 6-week experimental period, we will calculate frequency of cannabis use as the number of days used per week. To quantify change in frequency of cannabis use from baseline, change scores will be calculated by subtracting number of days per week of cannabis use during the 2-week baseline from those levels

recorded during each week of the mCM treatment period. A dichotomous variable will also be calculated reflecting whether a given participant achieved at least a 50% reduction in cannabis use during a given week. Thus, the data will be structured such that each participant will have up to 56 rows of data corresponding to each day of the 2-week baseline period and 6-week mCM/non-contingent control. Each row will contain a dichotomous indicator of whether or not cannabis was consumed that day, total quantity of cannabis consumed that day, total THC load of the cannabis used that day, daily estimates of functioning, a baseline estimate of cannabis use, and three variables capturing weekly varying frequency, quantity, and total THC load of cannabis use: the aforementioned dichotomous variable measuring whether a 50% reduction from baseline use was achieved and a change score, with a 0 change-score value for days falling during the 2-week baseline.

E.3. Hypotheses 1a and 1b.

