To examine the effect of reduced cannabis use on functioning assessed with EMA, day-by-day outcome variables will be modeled *via* MLM as a function of treatment group (Level 2), week (Level 1; with the two baseline weeks treated as a single week), and treatment-by-week interactions. Daily consumption (total equivalent number of joints/gram consumed and total potency; Level 1) will be examined as potential covariates. Linear and quadratic time effects will be explored. Week-by-week effects of cannabis reduction will be examined in separate models. We will also examine the effects of reduced use by modeling day-by-day and week-by-week outcomes as a function of week-by-week reductions in cannabis, independent of treatment group. Linear MLM will be used to model normally distributed outcome variables *via* PROC MIXED. Generalized linear MLM will be used to model dichotomous and otherwise non-normally distributed outcome variables *via* PROC GLIMMIX.

E.4. Supplementary Aim.

To examine whether reduced cannabis use moderates or is moderated by other factors (e.g., sex differences), the models examined in Hypotheses 1a and 1b will be modified to include potential Level-1 (e.g., day-to-day craving, sleep) and Level-2 (e.g., sex, baseline cannabis use, self-efficacy) predictors as well as their interactions with week-by-week change in cannabis use. For instance, to determine whether a week-by-week reduction in cannabis use moderates the association of day-by-day cannabis use (or abstinence) with daily working memory, whether or not participants used cannabis that day (Level 1) will be added as a predictor of working memory as will its interaction with week-by-week change in frequency or quantity of cannabis use. This particular model could thus determine whether cannabis users demonstrate greater cognitive functioning on abstinent days when they reduce their cannabis use.

E.5. Power Calculations.

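### For drugged driving, E.3's model on change in days of use is largely circular: fewer use days lower the outcome even if driving per use day is unchanged

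*Combined protocol and SAP*

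**What the plan says.** Hypothesis 1b (Specific Aims, R33 Aim 1) is worded as an association: "Decreased cannabis use will be associated with significant improvements in working memory, impulsivity, and drugged driving".

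Driving is measured in three ways:

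- **Diary item (D.6.1), conditional on use:** "If participants report use, they will also be asked if they drove a vehicle within two hours of use".
- **Nightly item (D.6.1), not conditional on cannabis:** the request reads "report the total number of times they engaged in any form of drugged driving during the past 24 hours at the end of each night".
- **Timeline Followback (Table 3), at baseline and 8 weeks:** participants "report days they have driven within 2 hours of using cannabis use in the past 28 days".

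E.2 aggregates the diary data to one row per day. Its list of day-level variables ends with "whether participants drove while intoxicated; and total amount of physical activity". It does not say which driving item feeds this variable. For frequency of use, "change scores will be calculated by subtracting number of days per week of cannabis use during the 2-week baseline" from the weekly level in the treatment period. E.2 also provides weekly variables for quantity and THC load.

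E.3 first models daily outcomes on treatment group, week and their interaction, with daily consumption as a possible covariate. It then adds models of daily and weekly outcomes "as a function of week-by-week reductions in cannabis, independent of treatment group". No section restricts driving to use days, records total driving, or specifies an offset.

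**The concern.** Distress, working memory, impulsivity and step counts can take any value on a day without cannabis. Driving within two hours of cannabis use cannot occur on such a day. A model of drugged driving on change in use days therefore has a component of the outcome as its predictor, and an association is expected even if nobody drives differently after using.

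The study is meant to support reduced use as a valid outcome measure in treatment trials. Validating reduced use against an outcome that contains use is circular. A significant coefficient could be reported as a functional gain when it only restates that there were fewer use days.

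**Working it through.** **The plan's own figures.** B.5 gives 17.5 use days per month falling to 10.3: 1 − 10.3/17.5 = 0.41, as stated. E.5 gives 90% power for r = .16 at an effective sample size of 60 × 7 = 420. By Fisher's z, atanh(.16) × √417 − 1.96 = 0.1614 × 20.42 − 1.96 = 1.34, so power is 0.91, which agrees. Nothing below depends on it, but it shows that weekly change in use is one of the exposures the study was sized on.

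**Identity.** Let u be the proportion of days with use and q the chance of driving within two hours on a use day. For the conditional item, P(drugged-driving day) = u × q. With q constant, the ratio after to before is u₁q/u₀q = u₁/u₀, whatever q is.

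- Pilot reduction, q = 0.3 (assumed): 7 × (17.5/30) × 0.3 = 1.23 days per week before, and 7 × (10.3/30) × 0.3 = 0.72 after, a 41% fall. The day-level odds ratio is (0.103/0.897)/(0.175/0.825) = 0.54.
- A 50% cut in use days gives a 50% fall. The odds ratio is 0.36 to 0.49 for q from 0.1 to 0.5 and baseline use from 40/90 of days (the entry minimum in C.3) to 6/7 of days (assumed).

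**Simulation.** There were 60 participants (taken as 40:20) with 56 days each. Baseline use was on 45–100% of days and the mean reduction under contingency management was 41%. Each person's q was fixed throughout (logit SD 1). The model was a logistic GEE with exchangeable correlation, standing in for PROC GLIMMIX, with 200 replicates per row. The exposure model regresses the daily outcome on weekly change in use days and baseline use. A fall is declared when p < .05 in that direction. The documents give no driving rates, so q is an assumption shown over a range.

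| Scenario, q unchanged over time | Exposure model, all days: fall declared | OR per day/week less use | Use days only: two-sided p < .05 | Randomised treatment-by-period: fall declared |
|---|---|---|---|---|
| q = 0.1 | 100% | 0.74 | 8.5% | 48.5% |
| q = 0.3 | 100% | 0.70 | 5.5% | 87.5% |
| q = 0.5 | 100% | 0.67 | 5.5% | 97.5% |
| q = 0.1, plus unrelated events on 5% of days | 100% | 0.84 | 6.5% | 30% |
| q = 0.3, plus unrelated events on 5% of days | 100% | 0.76 | 7.5% | 76% |
| q = 0.3, mean reduction set to zero | 100% | 0.75 | 9% | 4% |

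In the last row, ordinary week-to-week variation in use days is enough to drive the exposure model. Restricted to use days, the odds ratio is 1.00 in every row. Rejection there is close to 5% but somewhat above it in places (simulation standard error √(0.05 × 0.95/200) = 1.5 points).

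**Variants.**

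- Daily quantity as a covariate (assumed mean 1 g per use day, 100 replicates): a fall declared in 99% at q = 0.1 and 100% at q = 0.3, odds ratios 0.80 and 0.79.
- Weekly Poisson GEE on counts, mean q 30%, reductions of 0–90% in two thirds of people: 200/200 significant. With a log(use days) offset in weeks with use, 9/200 = 4.5%.
- Driving made to rise on the remaining use days (60 replicates, one assumed rise): still 100%, odds ratio 0.77.

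**The case against.** **Item.** The nightly question covers drugged driving of any kind, so alcohol or other drugs could produce a positive on a day without cannabis. The wording of the conditional item could also be read as following any reported substance. This stands as a limit: the outcome is not zero by definition on every non-use day unless the cannabis-conditional item defines it. Unrelated events dilute the artefact, but at 5% of days they did not remove it.

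**E.4.** The supplementary aim already sketches a model with same-day use and its interaction with weekly change. In a 60-replicate run with constant q and 2% background events, adding the same-day indicator cut rejection for weekly change from 100% to 5%. So a reader who infers that the study has no means of separating fewer use days from safer use days goes too far. But E.4's worked example is working memory, and driving is not named. If the cannabis-conditional item is the outcome, every non-use day is zero and the indicator separates perfectly, so restriction to use days is then needed.

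**Exposure.** E.3 speaks of reductions in cannabis, and E.2 also builds quantity and THC-load variables. The proportionality is derived for days of use only. Smaller amounts on the same number of use days carry no such identity, and those exposures were not simulated.

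**Estimand.** Fewer drugged-driving days is a real safety gain, and the Specific Aims motivate the outcome by traffic accidents. The randomised contrast also falls when use falls (48.5–97.5% in the first three rows). That is accepted: there it is a total effect of the intervention, and the contrast is quiet (4%) when use does not change. The exposure model is not.

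**Conclusion.** The point holds for drugged driving with change in days of use as the exposure. Under constant driving per use day, the association equals the proportional cut in use days (41% on the pilot figures), and the model declares a fall in about 100% of simulated trials for q from 0.1 to 0.5. The identity does not depend on the driving rate. The rejection rates rest on the assumed rates, their spread, baseline use and the GEE stand-in.

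A reader might infer that Hypothesis 1b cannot fail for driving, or will be declared supported whatever participants do. The documents do not support that. E.3 puts the randomised treatment-by-week model first and does not say that the exposure model decides the hypothesis. A large enough rise in driving on the remaining use days could shrink or reverse the association. What is established is narrower: this model can be significant with no change in driving per use day, so by itself it is not evidence of safer driving. The plan should be changed, at little cost.

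**What to change.** In E.2 and E.3:

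1. State which driving item defines the day-level outcome, and whether it covers cannabis only or any substance.
2. Make the randomised treatment-by-week comparison of drugged-driving days the driving test for Hypothesis 1b, read as a total effect that includes fewer use days.
3. Beside the exposure model, add a supportive day-level logistic analysis restricted to use days, or extend E.4's same-day-use model to driving where the chosen item allows it. Use a log(use days) offset only for weekly counts, in weeks with use; it is undefined in weeks without.
4. State that an association of total drugged-driving days with fewer use days is expected arithmetically and is not on its own evidence of safer driving.

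The cost is one extra model on data already collected. The downside is that the use-day analysis conditions on use after randomisation and has fewer records for people who reduce a lot, so it can only be supportive.
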